8.6 CYT107 Administration Permanently Discontinued

8.6.1 Reasons for CYT107 administration permanently discontinued

The investigator may interrupt study treatment at any time if a definite contraindication to treatment appears such as:

- Appearance of a critical event as defined in section 12.1
- Development of an exclusionary condition
- Requirement for prohibited concomitant medications
- If the patient or patient’s family decides to switch to comfort measure only and forgo life sustaining therapy.
- Patient request to terminate the study treatment
- Patient Informed Consent Withdrawal
- Patient withdrawn per other events at PI discretion

8.6.2 Procedure in case of CYT107 administration permanently discontinued

If a patient has a premature study treatment discontinuation for any reason, the subject may be retained in the study for data collection and testing procedures for remainder of the study period. If it is not possible, the last visit may include all tests and procedures scheduled for day29 visit plus a blood sample for detection of CYT107 immunogenicity (see appendix 2 Study flowchart). These data should be recorded in the research CRF.

The primary reason for withdrawal will be clearly documented in the patient’s medical record and recorded in the CRF.

In the specific case of patient consent withdrawal, the investigator must make every effort to perform the safety assessments.

Patients who are withdrawn from the study will be assigned appropriate alternative treatment as recommended by the PI in collaboration with the clinical team.

8.7 BLINDING

8.7.1 Organization of Blinding

The study will be performed in a double-blind manner. The patient, the investigator and study center staff will be blinded to study drug allocation. The pharmacist will be unblinded to study drug and will prepare study treatment or placebo for a patient as specified by the randomization scheme.

8.7.2 Unblinding

Emergency unblinding of the patient should only be undertaken by the investigator when it is essential to treat the subject safely and efficaciously. Most often, study drug discontinuation and knowledge of the possible treatment assignments are sufficient to treat a study subject who presents with an emergency condition. The investigator will make be responsible for making a decision to unblind in case of a suspected unexpected serious adverse reaction (SUSAR). The investigator will obtain the randomization assignment and a blinded alert will be sent to RevImmune, the coordinating center and the study team that a patient has been unblinded. The patient will be followed until resolution of the adverse event. All “end of study” assessments must be performed.

8.7.3 Final Unblinding

For every patient, the main study end points will be reached at day 60. Accordingly when the last patient of both IRIS-7A and IRIS-7B studies (i.e. the 30th patients of the two cumulated studies) will reach day 60, the database will be locked and the study unblinded for analysis.

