
Statistical methods and analysis
	
Descriptive statistics will include:
 
Quantitative variables: n, mean, standard deviation, minimum, maximum, 95% confidence intervals, median and quartiles will be presented when considered relevant
 
Qualitative variables: n and percent, and 95% confidence intervals when relevant
 
Inferential analyses
 
Categorical variables: The Fisher exact test or Pearson Chi-2 test (and Cochran-Mantel Haenszel procedure for adjusted inferences) as appropriate, will be used to compare rates of categorical variables between the two dosing frequency levels.
 
Continuous variables: parametric ANOVA (alternatives: non parametric ANOVA or transformation of the data / ANOVA for adjusted inferences) will be used to compare continuous variables between the two dosing frequency levels.
 
Primary Analysis of the Primary Objective
 
Primary endpoint: increase in absolute lymphocyte count (ALC) by 50% at Day 42

Duration of Patient participation
	
Patients are treated with CYT107 or control for 4 weeks and laboratory studies obtained for an additional 2 weeks up to approximately 42 days (Appendix 2, Flow Chart).
 
Patient outcomes will be followed at approximately 29, 42, 60, 90, 180 and 365 days to record data including incidence of new secondary infections, patient disposition, (i.e., discharged to home, skilled care facility, or long term health care facility), and readmissions to hospital, ICU days, and mortality.

Abbreviations

ADA	Anti-Drug Antibodies
AICD	Activation induced cell death
AE	Adverse effects
ARV	Anti-retroviral
CCR5	CC chemokine receptor type 5
CD	Cluster of differentiation
CHO	Chinese hamster ovary
CMV	Cytomegalovirus
CRF	Case report form
CRO	Contract research organization
CROI	Conference on retroviruses and opportunistic Infections
CRP	C reactive protein
CTL	Cytotoxic T lymphocytes
CXCR4	CXC chemokine receptor type 4
CYT107	CHO recombinant-human-Interleukin-7
CYT 99 007	Escherichia Coli recombinant human-Interleukin-7
D	Day
DAIDS	Division of acquired immunodeficiency syndrome
eCRF	Electronic case report form
EDC	Electronic data capture
ELISA	Enzyme-linked immunosorbent assay
EMR	Electronic medical record
FAS	Full analysis activity dataset
GCP	Good clinical practice
GI	Gastro-intestinal
HAART	Highly active antiretroviral therapy
HCT	Hematopoietic cell transplantation
HIV	Human immunodeficiency virus
ICH	International conference on harmonization

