4.3.2 Secondary Biological Activity Study Endpoints

- 1) *PK Sessions*: Briefly each patient will be sampled on day 1 and day 22 at 0 (pre-dose), 1, 3, 5, 7, 9 and 24 hrs post CYT107 administration. Main PK parameters will be assessed including Model-independent PK analysis will be used to estimate Tmax, Cmax, half-life, clearance and area-under-the-curve (AUC).
- 2) *Pharmacodynamics effects on immune markers*: The investigative sites will also examine the effect of CYT107 to restore function of immune effector cells in patients with sepsis.
 - i. Effect of CYT107 to increase the percentage of patients reaching an ALC>1200 in each dosing group. (An ALC of 1200 represents the lower limit of normal for most hospital laboratories.)
 - ii. Effect of CYT107 on absolute numbers of CD4⁺T and CD8⁺T over the study period,
 - iii. Effects on circulating monocyte HLA-DR expression
 - iv. Effects on whole blood LPS-stimulated TNF- α
 - v. Assessment of CYT107 immunogenicity by detection and quantification of binding antibodies and detection of neutralizing antibodies in positive samples.
- 3) *Incidence and type of opportunistic secondary infections*: We will compare the effect of CYT107 to reduce hospital-acquired secondary infections in CYT107 septic patients versus a control group of septic patients who receive placebo. The rate of hospital-acquire secondary infections at day 42 is ~ 40%.(20) We postulate that CYT107 will reduce the rate of secondary infections by ~ 30-40%. We will also examine other clinical measures in the CYT107-treated septic patients and compare outcomes including: SOFA scores, ICU free days, hospital free days, ventilator free days, decrease

in readmissions to ICU for recurrent infections. We will also record at approx. 60, 90, 180 and 365 day (1 year) general health status and survival.

All end points will be evaluated in a global analysis, pooling the results of the US and French sites using REDCap as the common patient database. Results will be visible to all investigative centers.

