4.4 Duration of the study

Patients will be treated with CYT107 or placebo for 4 weeks duration and undergo laboratory monitoring of various organ functions as detailed previously for the 28 days following the initial treatment. The ALC will be followed for an additional 14 days due to continuing effects of CYT107. Primary end points will be measured at approximately Day 42 +/- 3 days. Patient outcomes regarding secondary infections, readmission to hospitals, mortality, etc. will be followed at approximately 60, 90, 180 and 365 days after CYT107 therapy is initiated. Long term survival (1 year survival) will be recorded using a variety of means including physician records, patient telephone communication, and searches of mortality databases.

5. Study Population

5.1 Inclusion Criteria:

- 1) Patients of age ≥ 18 yrs to 80 yrs
- 2) Patients with persistent suspected sepsis at 48-120 hrs after admission
- 3) Two or more criteria for the systemic inflammatory response syndrome (SIRS) (see reference (19) for SIRS criteria) and a clinically or microbiologically suspected infection.
- 4) At least one organ failure as defined by a SOFA score of ≥ 2 at any time point during the 48-120 hrs after admission to the ICU
- 5) Requirement of vasopressor treatment as follows: i) epinephrine or norepinephrine at ≥ 0.05 $\mu\text{g}/\text{kg}/\text{min}$ ideal body weight; ii) vasopressin, or iii) dopamine at $\geq 4-5$ $\mu\text{g}/\text{kg}/\text{min}$ ideal body weight, continuously for 4 hrs or more, provided that at least 20 ml/kg of ideal body weight of crystalloid or an equivalent volume of colloid was administered during the 24-hour interval surrounding the start of vasopressor treatment, to maintain systolic pressure ≥ 90 mmHg or a mean arterial pressure ≥ 60 mmHg at any time point during their sepsis course preceding enrollment into the CYT107 study.
- 6) Lymphopenia with an absolute lymphocyte count ≤ 900 cells/ mm^3 at either the day of consent or the day prior to consent during their ICU stay
- 7) Predicted length of stay in the ICU of up to two weeks after starting drug therapy treatment in the trial
- 8) Ability to obtain a signed informed consent from patient or LAR consent.

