6.4 Procedure for Days 60, 90, 180 and One Year Follow-up Period

Patients will be followed for 60, 90, 180 and 365 day outcomes regarding disposition, i.e., incidence of new secondary infections, long term status, i.e., still hospitalized, discharged to long term care facility or nursing home, discharged to home, and mortality.

Systematic blood sample for Immunogenicity testing at D60, repeated at day 180 and 360 if not negative for anti-CYT107 antibodies.

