9.3 Statistical Analysis Plan

A Statistical Analysis Plan (SAP) will be written, validated and signed before the first interim analysis. This document will describe the detailed methodology for statistical analyses of the data collected in both US and French studies.

An interim analysis will be performed when the last patient of both IRIS-7A and IRIS-7B studies (i.e. the 30th patients of the two cumulated studies) will reach day 60, then the database will be locked and the study unblinded for analysis.

Final analysis including follow up controls will be performed when the last patient of both IRIS-7A and IRIS-7B studies (i.e. the 30th patients of the two cumulated studies) will reach day 360, then the database will be definitively locked for final data analysis.

10. Trial Organization

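### The day-60 unblinding precedes the day-90, 180 and 365 follow-up, and the plan does not say who stays masked

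*Protocol*

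**What the plan says.** **Blinding.** Protocol 8.7.1 blinds the patient, the investigator and centre staff; only the pharmacist knows the allocation. The synopsis adds outcome assessors.

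**Unblinding.** Section 8.7.3 reasons that "the main study end points will be reached at day 60". The trigger is the date on which "the last patient of both IRIS-7A and IRIS-7B studies (i.e. the 30th patients of the two cumulated studies) will reach day 60". What happens on that date is stated as follows: "the database will be locked and the study unblinded for analysis". Section 9.3 describes the same event as an interim analysis and sets a final lock at day 360.

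**Later follow-up.** The synopsis says: "Patient outcomes will be followed at approximately 29, 42, 60, 90, 180 and 365 days to record data including incidence of new secondary infections", together with disposition, readmissions, ICU days and mortality. Section 4.4 agrees: "Patient outcomes regarding secondary infections, readmission to hospitals, mortality, etc. will be followed at approximately 60, 90, 180 and 365 days". Section 6.4 lists "incidence of new secondary infections, long term status" and mortality. Section 4.2 obtains the later data by telephone interview, physician records or database searches. It also predicts fewer new infections and readmissions and better survival to one year.

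**Access to results.** After describing the pooling of both countries' data, 4.3.2 says: "Results will be visible to all investigative centers". Section 10.1 seats an investigator from each centre on the steering committee, which may be asked to evaluate interim results.

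**Infection panel.** Sections 3.2.3 and 10.3 use three blinded physicians from outside the investigative team.

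The SAP says nothing about blinding or about the timing of the two analyses.

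**The concern.** One event is headed as the final unblinding in 8.7.3 and called interim in 9.3, and up to 305 further days of outcome collection follow it. The plan does not say who receives the assignments, nor that anyone remains masked.

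Whether a new infection is recognised and reported, and where a patient is discharged, depends partly on the judgement of the person asking and the person answering. If either knows the arm, reporting can shift in the direction that the protocol itself predicts. The panel can only adjudicate the cases brought to it, and it does not adjudicate readmission or disposition.

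The words about unblinding for analysis do not settle the matter. Under 13.4 the coordinating centre does all data management and statistics, and under 4.1 and 4.2 it is also an enrolling site. No separation between the two functions is described.

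**Working it through.** The documents give no figure for this point, so there is none to reproduce. The check is the order of events, followed by a count of the contacts that fall after unblinding.

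**Inputs.** Unblinding is at day 60 of the last patient (8.7.3, 9.3). Later contacts are at days 90, 180 and 365 (synopsis, 4.4, 6.4). The number of patients is taken as 30. The last dose is on day 25 (8.5). Expected mortality is about 45% at 60 days (2.5). Accrual time is not given and is assumed.

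**Step 1: count.** Spread 30 entries evenly over *A* days, so the gap is *d* = *A*/29. On the unblinding date, the patient who is *j* places before the last (*j* = 0 to 29) is on day 60 + *jd*. That patient's day-*v* contact is still to come if *j* < (*v* − 60)/*d*.

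- 12 months: *d* = 365/29 = 12.59. Day 90: 30/12.59 = 2.38, so 3 patients. Day 180: 120/12.59 = 9.53, so 10. Day 365: 305/12.59 = 24.23, so 25.
- 24 months: *d* = 730/29 = 25.17. Day 90: 1.19, so 2. Day 180: 4.77, so 5. Day 365: 12.12, so 13.

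Faster accrual raises the counts. The staggering rule in 4.2 (second dose on day 4, plus 24 hours) means at least 4 days between patients if there is a single queue, so *A* is at least 29 × 4 = 116 days. The last column is the sum of max(0, 305 − *jd*) divided by 30 × 305.

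| Assumed accrual (days) | Day 90 | Day 180 | Day 365 | Share of day 60–365 window after unblinding |
|---|---|---|---|---|
| 116 | 8/30 | 30/30 | 30/30 | 81% |
| 180 | 5/30 | 20/30 | 30/30 | 70% |
| 365 | 3/30 | 10/30 | 25/30 | 42% |
| 730 | 2/30 | 5/30 | 13/30 | 22% |

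For *v* = 42 or 60, (*v* − 60)/*d* is not positive, so no day-42 or day-60 contact falls after unblinding.

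**Step 2: deaths.** If 45% have died by day 60, regardless of order of entry, multiply by 0.55. With 12 or 24 months this gives 1.7 or 1.1 contacts at day 90, 5.5 or 2.8 at day 180, and 13.8 or 7.2 at day 365. Later deaths reduce these further. Evaluable patients must complete two weeks of treatment, so their mortality may be below 45%.

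**Step 3: the trigger.** Sections 8.7.3 and 9.3 gloss the last patient as "i.e. the 30th patients of the two cumulated studies". Sections 4.2, 6.2 and 11.1 replace non-evaluable patients until each arm has at least 10 evaluable. One non-evaluable patient therefore makes the last randomised patient at least the 31st. Simulating blocks of three, with country strata ignored, the mean number randomised is 32.7 at an assumed 5% non-evaluable and 41.1 at 20%. Reading the gloss as the 30th evaluable patient does not fully cure this, because 30 can be reached with one arm at 9 and another at 11.

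**The case against.** The best defence is that the endpoints that matter are safe. The primary lymphocyte endpoint and the secondary-infection hypothesis are both set at day 42. For the later time points, 4.3.2 itself names only general health status and survival, and the SAP specifies no test of infections, readmissions or disposition after day 60. Mortality is hard to bias. All of this stands, and it confines the point to the later judgement-based outcomes. It does not remove the point, because 4.2 predicts benefit on infections and readmissions and the plan collects both to one year.

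Some stronger readings are tempting but are not supported:

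- *Replacement patients will be dosed after unblinding.* The operative trigger is the last patient. On that reading every replacement has reached day 60, well past the last dose on day 25. The stronger reading needs the parenthetical 30th to be taken as a count of randomised patients. The supportable finding is two descriptions that must be reconciled.
- *Follow-up staff will know the arm.* The text says unblinded for analysis. It does not say that sites, patients or callers receive assignments, and the blinding of centre staff and of the panel has no stated end date. Site knowledge is possible and unguarded, not certain.
- *Section 4.3.2 releases arm-level results at day 60.* The sentence carries no date and does not mention allocation.

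It can also be argued that withholding all aggregate results from investigators for a year is hard to justify in a small phase II study. That is fair: masking needs individual assignments to be withheld, not every summary.

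**Conclusion.** The concern holds in limited form. As written, the study is unblinded at the day-60 analysis while infections, readmissions and disposition are still being collected, and nothing states who remains masked. With even entry of 30 patients over an assumed 12 to 24 months, and before allowing for deaths, 3 to 2 of 30 contacts at day 90, 10 to 5 at day 180 and 25 to 13 at day 365 are exposed. Faster accrual raises these counts and deaths lower them. No size of bias can be derived from the documents. The day-42 endpoints are unaffected when the trigger is the last patient. The mismatch between the last and the 30th patient is a separate wording conflict. This should be changed, because the change is cheap and the later outcomes are ones on which the protocol predicts benefit.

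**What to change.** - **8.7.3 and 9.3:** state that at the day-60 lock individual assignments go only to the analysing statistician and the DSMB. Patients, site staff, follow-up callers and the infection panel stay masked to individual assignments until the last patient's final follow-up. Because the coordinating centre also enrols, say that the statistician is separate from its site team.
- **10.1 and 4.3.2:** let interim results reach investigators only in aggregate form that does not reveal any individual's allocation.
- **Trigger in 8.7.3 and 9.3:** define it as day 60 of the last randomised patient, replacements included, so that it agrees with 4.2, 6.2 and 11.1.

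Emergency unblinding under 8.7.2 is untouched. The cost is wording. The downside is that site staff learn individual assignments about 10 months later (365 − 60 = 305 days). If the sponsor had meant to count 30 randomised patients, the day-60 analysis would also wait for the replacements.

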8.8 Concomitant treatments

8.8.1 Steroids

Patients enrolled in this clinical trial may be receiving steroids; this will be limited to hydrocortisone at a dose no higher than 300 mgs of hydrocortisone daily.

8.8.2 Prohibited Medications

Are as follows:

- Concurrent immunotherapy; including growth factors, cytokines and interleukins other than the study medication, for example IL-2, Interferons, HIV vaccines, immunosuppressive drugs, hydroxyurea, immunoglobulins, adoptive cell therapy;
- Any investigational agent;
- Systemic corticosteroids other than hydrocortisone at a dose of 300 mgs/day.
- Biological agent (other cytokines such as IL-2, growth factor, monoclonal antibody);
- Cytotoxic chemotherapy

If it becomes obvious, during the course of the study, that administering any of these therapies are not in the patient's best interest, due to the patient's imminent demise or the patient or the patient's family desire to switch to comfort measures only, (i.e., not to continue aggressive care), then study drug treatment will be discontinued. (See section 7.8.2 for details on procedures to follow in case of study drug discontinuation).

9.0 Statistical Analysis

9.1 Sample Size

Sample size justification

The primary endpoint of this trial is to compare two different dosing regimens of CYT107 to increase the absolute lymphocyte count (ALC), a marker of immunosuppression in sepsis which correlates with mortality. Although CYT107 has not been previously been used to treat patients with sepsis, there are data on the effect of CYT107 to increase the absolute numbers of CD4 and CD8 T cells in patients with cancer and in patients with HIV (see Figs 2&6 and reference #14). As demonstrated in Figs 2 & 6, CYT107 at a dose of 10 micrograms/kg (the dose that will be used in the present study) has a very predictable effect to cause a doubling of the number of CD4 T cells which are a major component of the absolute lymphocyte count (ALC) in patients with HIV. This effect to increase the absolute numbers of CD4 T cells was consistent in almost all patients who were treated with CYT107. CYT107 has a similar effect (although not quite as pronounced) on CD8 T cells. Therefore, we anticipate that greater than 80% of septic patients who are treated with CYT107 at a dose of 10 micrograms/kg (either high frequency dosing regimen or the low frequency CYT107 dosing regimen) will increase their ALC by over 50% by day 42, whereas less than 20% of patients who receive placebo will exhibit such a change. Under these assumptions, a simulation-based power calculation as implemented using the primary analytical plan listed in section 9.3.2. In particular, the proposed study design (10 subjects per treatment arm) was found to have greater than 85% power to detect an equal or more extreme treatment effect. Thus, we believe that 10 patients per group is sufficient to show a statistically significant effect of CYT107 to increase the ALC by over 50%.

Two other major goals of the study are to establish the safety of CYT107 in patients with sepsis and to determine that the pharmacokinetics and pharmacodynamics are not significantly altered in septic patients. CYT107 has been administered to over 300 patients and has been well tolerated with a low incidence of side effects. (see Investigator's brochure.)

9.2 Statistical Analysis

9.2.1 Analysis Datasets

9.2.1.1 Definition of protocol deviations

Major protocol deviations are defined as deviations liable to bias the evaluation of the main study endpoint. The following deviations will be considered major:

- Noncompliance with the inclusion or exclusion criteria
- Noncompliance with study treatment
- Intake/administration of prohibited medication(s)

All other deviations will, a priori, be considered as minor deviations. However, all deviations will be reviewed during a data review meeting before data base lock and statistical analysis. This data review will also serve to constitute the analysis datasets.

